A dental hygienist will professionally clean each subject's teeth using a conventional dental prophylaxis paste followed by flossing (carried out by the hygienist) to remove all visible stain, plaque, debris, and all sub- and supra-gingival calculus from the anterior teeth. A second dental examiner will confirm all sub- and supra-gingival calculus, visible stain (Total MLSI (A×I) = 0), plaque and debris has been removed from the facial, palatal/lingual surfaces of the anterior teeth (visually and by tactile assessment using a dental explorer). Subjects will then be requested to brush twice daily (morning and evening) with their allocated study dentifrice for the next 4 weeks. They will receive verbal and written product usage instructions. First product use will be supervised on site, with a further supervised brushing at Visit 3. Subjects will be asked to record each product use in a diary, and note any significant changes to diet or smoking status, medications and health during the course of the study, and confirmed by the site at each visit.

Subjects will return to the site at Visits 3 and 4, having abstained from oral hygiene for at least 6 hours prior to their visit. Subjects will brush their anterior teeth for 30 seconds using a wetted toothbrush, prior to undergoing a full MLSI stain assessment. Subjects will be asked to bring their study dentifrice, toothbrush and completed diary card to each visit to facilitate compliance checks.

Randomised subjects who request so will be offered a full mouth dental prophylaxis on completion of Visit 4 procedures, or on completion of the visit where they exit the study.

Repeat examinations will be performed by the dental examiner at each full MLSI assessment visit. Ten subjects will be randomly selected for repeat examinations across each assessment window (a total of 30 repeat examinations over the duration of the study) at Visits 2 (pre-prophylaxis), 3 and 4. There will be a minimum of 10 minutes, and a maximum of 30 minutes between repeatability examinations.

Study Schedule

Procedure	Pre-screening	Visit 1 Screening	Visit 2 Baseline (Day0)	Visit 3 Week 2 (Day14 ± 2)	Visit 4 Week 4 (Day28 ± 2)
Telephone Screening of Subjects	✓				
Inform Consent		✓			
Demographics, Medical History, Smoking Status		✓			
Current / Concomitant Medication		✓	✓	✓	✓
Oral Soft Tissue (OST) Examination		✓	✓		
Full Oral Hard Tissue (OHT) Examination		✓	✓		
Visual MLSI Stain Assessment		✓			
Inclusion / Exclusion Criteria		✓	✓		

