1.4 Sample Size Calculation

A sufficient number of subjects will be screened to randomise at least 220 subjects to ensure 200 evaluable subjects complete the study. This will ensure approximately 50 evaluable subjects per treatment arm. This study has not been formally powered to make any claims, and is appropriately sized as a PoP study for the purpose of observing meaningful trends.

2 Planned Analyses

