4.4.1.2 Statistical Hypothesis, Model, and Method of Analysis

Summary statistics including mean, SD, median, min, max will be provided for baseline and Week 4 by randomised treatment group ([Table 14.2.1.1.1](#)). The overall MLSI score at Week 4 will be analysed using analysis of covariance (ANCOVA) with treatment and smoking status (smoker/non-smoker) as factor and pre-prophylaxis baseline overall MLSI score as covariate.

The primary comparisons are

- Test dentifrice (RDA-58) vs. Reference dentifrice (RDA-80)
- Test dentifrice (RDA-77) vs. Reference dentifrice (RDA-80).

All other comparisons associated with secondary and exploratory objectives will also be presented under the same analysis, namely

- Test dentifrice (RDA-58) vs. Reference dentifrice (RDA-120) (secondary)
- Test dentifrice (RDA-77) vs. Reference dentifrice (RDA-120) (secondary)
- Reference dentifrice (RDA-120) vs. Reference dentifrice (RDA-80) (secondary)
- Test dentifrice (RDA-58) vs. Test dentifrice (RDA-77) (exploratory)

Adjusted means of all treatments will be provided. Treatment differences of above mentioned comparisons will be provided together with their 95% CIs and p-values ([Table 14.2.1.1.2](#)). The assumption of residual normality in ANCOVA analysis will be investigated. If violated, data transformation or a non-parametric method (e.g., the Wilcoxon rank sum test) will be applied.

There will be no multiplicity adjustment for treatment comparisons as this study is an exploratory POP study.

Efficacy will be evaluated based on the ranking performance of the study treatments on the stain variables. The minimum requirement will be similar, or lower levels of stain for at least one of the experimental products compared to the standard fluoride dentifrice (Colgate Cavity Protection[®]). The marketed SnF₂ dentifrice (Sensodyne Complete Protection) will be expected to demonstrate a comparable, or statistically significantly better performance on the stain variables versus the experimental products and Colgate Cavity Protection[®].

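### All six pairwise intervals use one residual variance pooled over four arms, and only normality is checked; if the arms differ in spread, some 95% intervals will be too narrow and others too wide

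*SAP*

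**What the plan says.** SAP 4.4.1.2 sets the model: "The overall MLSI score at Week 4 will be analysed using analysis of covariance (ANCOVA) with treatment and smoking status (smoker/non-smoker) as factor", with pre-prophylaxis baseline overall MLSI as covariate. The two primary, three secondary and one exploratory comparisons all come from this fit. SAP 4.6 uses the same model for the exploratory scores.

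On output: "Treatment differences of above mentioned comparisons will be provided together with their 95% CIs and p-values". On assumptions: "The assumption of residual normality in ANCOVA analysis will be investigated". On what follows: "If violated, data transformation or a non-parametric method (e.g., the Wilcoxon rank sum test) will be applied". SAP 4.4.1.3 and Protocol 9.3.2 repeat this check and fallback. Neither document mentions equality of variance, arm-specific residual variances or robust standard errors. SAP 4.4.1.2 and the shell of Table 14.2.1.1.1 give SDs by arm, but no action depends on them.

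SAP 1.1 has a second examiner confirm after prophylaxis that no stain remains: "visible stain (Total MLSI (A×I) = 0". Every subject therefore restarts at the floor of the scale.

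**The concern.** A standard ANCOVA estimates one residual variance from all arms and uses it for every pair. With about 50 subjects per arm, moderate non-normality does little harm to intervals for mean differences. Unequal spread can do more, because the interval for one pair borrows its variance from two arms that are not in that pair.

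Unequal spread is plausible here. The score starts at zero and is bounded below. Protocol 3.3 expects little stain build-up on the facial surfaces compared with the lingual ones, and facial surfaces are 12 of the 18 scored (12 facial, 6 lingual). Many site scores should thus stay near the floor, and an arm that builds up more stain may also vary more. The documents state no such relation.

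What is at stake is the calibration of the intervals and p-values reported for every comparison. The plan sets no margin for when two products count as similar in stain, so readers will lean on interval width.

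**Working it through.** **Inputs**

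- Subjects: "A sufficient number of subjects will be screened to randomise at least 220 subjects to ensure 200 evaluable subjects complete the study" (SAP 1.4). 200/4 = 50 per arm, which matches the plan. The loss allowed for is 20/220 = 9.1%. There is no power calculation, effect size or SD to reproduce.
- Level: two-sided 95% intervals (SAP 4.4.1.2).
- Allocation: taken as equal across arms.
- SD ratios of 1.25, 1.5 and 2 (high-variance to low-variance arm): assumptions, because the documents give no SDs.

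**Formulas**

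With equal n, the pooled variance P is the mean of the four arm variances. For arms i and j the model takes the variance of the difference as 2P/n. The true value is (v_i + v_j)/n. So

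- width ratio w = sqrt[2P / (v_i + v_j)], the interval reported relative to the correct one;
- coverage = 2Φ(1.96w) − 1.

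The sample size cancels.

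**Worked case: one arm at SD ratio 1.5**

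- P = (2.25 + 1 + 1 + 1)/4 = 1.3125.
- High versus low: w = sqrt(2.625/3.25) = 0.899, coverage 92.2%.
- Low versus low: w = sqrt(2.625/2) = 1.146, coverage 97.5%.

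**Worked case: two arms at SD ratio 1.5**

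- P = (2.25 + 2.25 + 1 + 1)/4 = 1.625.
- High versus low: w = sqrt(3.25/3.25) = 1, coverage 95.0%.
- High versus high: w = sqrt(3.25/4.5) = 0.850, coverage 90.4%.
- Low versus low: w = sqrt(3.25/2) = 1.275, coverage 98.8%.

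**Coverage of the nominal 95% interval, all cases**

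| High-variance arms | Pair | ratio 1.25 | ratio 1.5 | ratio 2 |
|---|---|---|---|---|
| one | high vs low | 93.6% | 92.2% | 89.9% |
| one | low vs low | 96.4% | 97.5% | 99.0% |
| two | high vs low | 95.0% | 95.0% | 95.0% |
| two | high vs high | 92.4% | 90.4% | 87.9% |
| two | low vs low | 97.3% | 98.8% | 99.8% |
| three | high vs low | 96.1% | 96.8% | 97.5% |
| three | high vs high | 93.8% | 93.1% | 92.3% |

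**Check by simulation**

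The planned ANCOVA was simulated with 50 per arm, smoking factor, baseline covariate, normal errors and 6,000 runs, for one arm at each ratio and two arms at 1.5 and 2. Coverage agreed with the formula to within 0.9 of a percentage point. Robust (HC2) standard errors on the same data gave 94.1% to 95.5% for every comparison. HC3 also gave about 95% throughout, and its intervals were about 1% wider when all variances were equal.

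**Would the planned check notice?**

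With one high-variance arm and normal errors, a Shapiro-Wilk test on the residuals rejected in 7%, 17% and 69% of runs at ratios 1.25, 1.5 and 2. A Levene test by arm rejected in 29%, 76% and 100%. With skewed (gamma) outcomes whose SD is proportional to the mean, Shapiro-Wilk rejected in about 95% of runs or more, for assumed coefficients of variation from 0.4 to 1.0.

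**The case against.** The strongest reply is that the plan already has a trigger. A score with a floor at zero and spread rising with its mean is usually right-skewed. The normality check would then nearly always fail, and a transformation often steadies the variance too. The first half stands, as the gamma simulation shows. But the response is an open choice. A transformation may or may not equalise spread, and it moves the difference off the MLSI scale. A Wilcoxon test does not address unequal spread and drops the adjustment for baseline and smoking. Neither assures calibrated intervals for the adjusted differences the plan reports.

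Second, "Efficacy will be evaluated based on the ranking performance of the study treatments on the stain variables", and the ranks of the adjusted means do not depend on how their standard errors are computed. The study is unpowered, and "There will be no multiplicity adjustment for treatment comparisons as this study is an exploratory POP study". This limits the consequence and is why the point is minor. It does not cover the intervals and p-values.

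Third, both test products are SnF₂/STP formulations of lower abrasivity than the marketed SnF₂ product, so they may share the larger variance. The primary intervals then keep 95%. This stands, and it rules out saying that the primary intervals will be too narrow.

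Two stronger readings are tempting:

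- A reader might take 6.4%, 7.8% and 10.1% (100 minus 93.6, 92.2 and 89.9) as false-positive rates for a primary comparison. If an arm is more variable because it stains more, its mean differs and the null hypothesis is false. The figures are then non-coverage of an interval, not type I error.
- A reader might infer that the trial is designed to find one low-abrasivity arm staining more than the rest. SAP 4.4.1.2 and Protocol 9.2.4 ask instead that at least one test product stain no more than the fluoride reference.

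**Conclusion.** The gap in the plan is real: one pooled variance, six intervals, and a check on normality alone. Its effect is conditional. With one high-variance arm, coverage against another arm drops by 1.4 to 5.1 points (95 minus 93.6 and 89.9), while intervals between low-variance arms are about 7% to 32% wider than they need be. With two high-variance arms, the high-versus-low comparisons are unaffected and the error moves to the pairs within each group. With three, high-versus-low intervals are too wide.

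In every unequal-variance pattern examined, at least one pre-listed comparison is miscalibrated. Which one cannot be known in advance, and that favours a rule fixed before unblinding. The sizes rest on assumed SD ratios and equal arm sizes. The ranking of products is not affected. This is a cheap improvement, not a flaw that threatens the study's purpose.

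**What to change.** Keep the ANCOVA with the same factors and covariate. Add to SAP 4.4.1.2, and by reference to 4.6, one of these for the differences, intervals and p-values in Table 14.2.1.1.2 and the corresponding exploratory tables:

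- HC3 standard errors, which leave the point estimates unchanged; or
- arm-specific residual variances (group = treatment) with Kenward-Roger degrees of freedom, which reweight the fit and may shift the adjusted means slightly.

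If the sponsor prefers the pooled-variance model as the main analysis, pre-specify one of these as a sensitivity analysis. Add a check of residual variance by arm beside the normality check, and say how the two sets of intervals will be read if they differ.

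The cost is one model option and a sentence in the SAP. No extra data or subjects are needed. The downside is HC3 intervals about 1% wider if the variances are in fact equal.

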Stain assessments will be made on the facial and lingual surfaces of the anterior teeth as these surfaces are considered the most aesthetically important with respect to dental stain accumulation. Dental stain largely builds up in the harder to reach interproximal areas, therefore in addition to analysis of the total MLSI (A×I) the interproximal regions have also been given focus as an exploratory objective in this study. As most of the stain is removed from the body and gingival regions, we would expect to see little change in the total gingival MLSI (A×I) and total body MLSI (A×I), therefore, these variables are not being analysed in this study. Furthermore, separate analysis of the facial and lingual surfaces are not of focus in this study. As the facial teeth are the most brushed we would expect to see little stain build up on the facial surfaces in comparison to the lingual surfaces, with little difference expected between the total MLSI (A×I) and total lingual MLSI (A×I).

A single examiner will perform the dental stain assessments for all subjects at the baseline, Week 2 and 4 visits to avoid inter-examiner variability. To assess the repeatability of the stain assessments 30 repeat examinations will be performed by the dental examiner over the duration of the study.

The dosage regimen of twice daily use (morning and evening) will be the same for all subjects, and has been selected based on widely recommended oral hygiene practice, and typical consumer habit.

Document Name	207872 Clinical Protocol.doc		
Type	Version	Document Identifier	Effective Date
elido_clinical_doc	5.0; Most-Recent; Effective; CURRENT	090032d580d488e0	30-May-2017 04:37:09
Reason For Issue	Auto Issue		

Sensodyne Complete Protection has been selected as a reference dentifrice in this study as it is a commercialised SnF₂ containing dentifrice. Colgate Cavity Protection® has been selected as a reference comparator as it is marketed globally, does not contain any ingredients known to impart extrinsic dental stain, and is considered to be representative of a moderate abrasivity standard, daily use fluoride dentifrice. Two recent stain build up studies have been conducted by GSKCH, which contain both the commercialised SnF₂ dentifrice and Colgate Cavity Protection®, providing us with a recent benchmark of relative and expected performance at the Week 4 time-point.

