9.3.2. Primary Analysis

The primary variable will be overall MLSI at Week 4. This variable will be analysed using analysis of covariance (ANCOVA) with treatment and smoking status as factor, and pre-prophylaxis baseline mean MLSI score as the covariate. Adjusted means and treatment differences between the two test products and the marketed standard fluoride dentifrice, and the treatment difference between the marketed SnF₂ dentifrice and the marketed standard fluoride dentifrice will be provided together with their 95% CIs and p-values.

The assumption of residual normality in ANCOVA analysis will be investigated. If violated, data transformation or a non-parametric method (e.g., the Wilcoxon rank sum test) will be applied.

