3.2 Subgroups/Stratifications

Eligible subjects will be stratified by baseline total MLSI (A×I) score (Low: <45; High: ≥45) and smoking status into four strata in study treatment randomization.

- MLSI Score High (≥45), Smoker
- MLSI Score Low (<45), Smoker
- MLSI Score High (≥45), Non Smoker
- MLSI Score Low (<45), Non Smoker

Subjects identified as being in the wrong strata will be placed in correct strata prior to analysis and will also be considered for protocol deviations and potential exclusion from a PP analysis.

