n	XX	XX	...	XX
MEAN	XX.X	XX.X	...	XX.X
SD	XX.XX	XX.XX	...	XX.XX
MEDIAN	XX.X	XX.X	...	XX.X

CCI

207782

Statistical Reporting and Analysis plan, 24 Aug 2017

	Test Dentifrice (RDA-58) (N=XX)	Test Dentifrice (RDA-77) (N=XX)	Overall (N=XX)
MINIMUM	XX	XX	...	XX
MAXIMUM	XX	XX	...	XX
STRATIFICATION				
MLSI HIGH, SMOKER	xx (xx.x)	xx (xx.x)	xx (xx.x)	xx (xx.x)
MLSI LOW, SMOKER	xx (xx.x)	xx (xx.x)	xx (xx.x)	xx (xx.x)
MLSI HIGH, NON-SMOKER	xx (xx.x)	xx (xx.x)	xx (xx.x)	xx (xx.x)
MLSI LOW, NON-SMOKER	xx (xx.x)	xx (xx.x)	xx (xx.x)	xx (xx.x)

Page x of y

PPD

CCI

207782

Statistical Reporting and Analysis plan, 24 Aug 2017

Protocol 207872

Program Run Date:xxxx

Table 14.2.1.1.1
Summary of Overall MLSI (AXI) Score
Intent-to-Treat Population

Intent-to-Treat Population (N=XX)

Visit		Test Dentifrice (RDA-58) (N=XX)	TestDentifrice (RDA-77) (N=XX)	Reference Dentifrice (RDA-80) (N=XX)	Reference Dentifrice (RDA-120) (N=XX)	Overall (N=XXX)
Baseline	N	Xx	Xx	xx	Xx	xx
	MEAN	x.xx	x.xx	x.xx	x.xx	x.xx
	SD	x.xxx	x.xxx	x.xxx	x.xxx	x.xxx
	SE	x.xxx	x.xxx	x.xxx	x.xxx	x.xxx
	MEDIAN	x.xx	x.xx	x.xx	x.xx	x.xx
	MINIMUM	X.xx	X.xx	x.xx	X.xx	x.xx
	MaxIMUM	X.xx	X.xx	x.xx	X.xx	x.xx
Week 2	N	Xx	Xx	xx	Xx	
	MEAN	x.xx	x.xx	x.xx	x.xx	
	SD	x.xxx	x.xxx	x.xxx	x.xxx	
	SE	x.xxx	x.xxx	x.xxx	x.xxx	
	MEDIAN	x.x	x.x	x.x	x.x	
	MINIMUM	X.x	X.x	x.x	X.x	
	MAXIMUM	X.x	X.x	x.x	X.x	
Week 4	Same as above					

Page x of y

PPD

CCI

207782

Statistical Reporting and Analysis plan, 24 Aug 2017

Protocol 207782

Program Run Date:xxxx

Table 14.2.1.1.2
Statistical Analysis of Overall MLSI (AXI) Score
Intent-to-Treat Population

Intent-to-Treat Population (N=XX)

Visit	Test Dentifrice (RDA-58) (N=XX)	Test Dentifrice (RDA-77) (N=XX)	Reference Dentifrice (RDA-80) (N=XX)	Reference Dentifrice (RDA-120) (N=XX)
Week 2	LSmean (SE) ^[1]	x.xx (x.xxx)	x.xx (x.xxx)	x.xx (x.xxx)
	Comparison^{[1],[2]}	Difference	95% CI-	P-value
	Test Dentifrice (RDA-58) vs Reference Dentifrice (RDA-80)	x.xx	(x.xx, x.xx)	0.xxxx
	Test Dentifrice (RDA-77) vs Reference Dentifrice (RDA-80)	x.xx	(x.xx, x.xx)	0.xxxx
	Test Dentifrice (RDA-58) vs Reference Dentifrice (RDA-120)	x.xx	(x.xx, x.xx)	0.xxxx
	Test Dentifrice (RDA-77) vs Reference Dentifrice (RDA-120)	x.xx	(x.xx, x.xx)	0.xxxx
	Test Dentifrice (RDA-58) vs Test Dentifrice (RDA-77)	x.xx	(x.xx, x.xx)	0.xxxx
	Reference Dentifrice (RDA-120) vs Reference Dentifrice (RDA- 80)	x.xx	(x.xx, x.xx)	0.xxxx
Week 4	Same as above			

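### The only non-parametric fallback named for the primary ANCOVA, the Wilcoxon rank sum test, drops baseline stain and smoking status; a covariate-adjusted fallback should be named instead

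*SAP*

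**What the plan says.** SAP 4.4.1.2 analyses the Week 4 overall MLSI score by "analysis of covariance (ANCOVA) with treatment and smoking status (smoker/non-smoker) as factor and pre-prophylaxis baseline overall MLSI score as covariate". On outputs it says: "Treatment differences of above mentioned comparisons will be provided together with their 95% CIs and p-values." The shell for Table 14.2.1.1.2 has least-squares means, differences, intervals and p-values, with a footnote attributing them to that ANCOVA.

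Residual normality is to be examined. SAP 4.4.1.2 continues: "If violated, data transformation or a non-parametric method (e.g., the Wilcoxon rank sum test) will be applied." SAP 4.4.1.3, headed as supportive analyses, repeats the sentence, and protocol 9.3.2 has the same rule: "data transformation or a non-parametric method (e.g., the Wilcoxon rank sum test) will be applied". None of the three places gives a criterion for violation, a named transformation, an order of preference, a time for the decision, or a statement of which result governs.

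On randomisation, SAP 3.2 begins: "Eligible subjects will be stratified by baseline total MLSI", and it adds smoking status as the second factor. The stratifying score is the total over facial surfaces only, cut at 45 (protocol 3.1, SAP 1.1). The ANCOVA covariate is the mean over facial and lingual sites (SAP 4.4.1.1).

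On interpretation, SAP 4.4.1.2 says: "Efficacy will be evaluated based on the ranking performance of the study treatments on the stain variables." The minimum requirement is that at least one experimental product shows similar or lower stain than the standard fluoride dentifrice.

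**The concern.** The Wilcoxon rank sum test compares two arms and uses nothing else. If it replaced the ANCOVA, the comparison would lose both terms that the primary model was built to include. One of these, smoking status, is a randomisation stratifier, and the other is closely related to one. The test produces no adjusted means. The shift estimate and interval that can accompany it (Hodges-Lehmann) are also unadjusted.

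The fallback could plausibly be reached. Teeth are cleaned to MLSI = 0, and the endpoint then averages up to 72 sites. Protocol 3.3 expects little change at gingival and body sites, which are half of them, and little facial build-up relative to lingual. Scores bunched near zero are therefore plausible, though the documents give no distribution.

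At stake is precision in a trial with about 50 evaluable subjects per arm. Because the choice is left open, it could also be made after results are known.

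**Working it through.** **The plan's own figures.** 200/4 = 50 evaluable per arm, and 220 randomised less 200 is 20, an implied loss of 20/220 = 9.1%. These are consistent. No power, effect size or SD is stated, so there is no power figure to reproduce.

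**Sites averaged.** (12 facial + 6 lingual surfaces) x 4 = 72 sites. Gingival and body sites are 18 x 2 = 36.

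**Large-sample guide.** If baseline and smoking explain a share R² of the Week 4 variance (assumed), the variance of an unadjusted difference exceeds the ANCOVA's by the factor 1/(1 - R²). Under normality, Wilcoxon has efficiency 3/π = 0.955 relative to the t-test. Its effective size per arm is therefore 50 x 0.955 x (1 - R²): 43 at R² = 0.09, 36 at 0.25 and 24 at 0.49.

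The effect that an ANCOVA detects with 80% power, in residual SD, is (1.960 + 0.842) x sqrt(2/50) = 0.560. At that effect, Wilcoxon power is Φ(2.802 x sqrt(0.955 x (1 - R²)) - 1.960):

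| R² | 0 | 0.10 | 0.25 | 0.36 | 0.49 |
|---|---|---|---|---|---|
| Wilcoxon power | 78% | 74% | 66% | 59% | 50% |

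**Simulation with skewed scores.** Because the fallback applies when residuals are not normal, the comparison was also simulated. Everything in this set-up except the sample size and the four strata is assumed:
- 50 per arm, blocks of 4 in four strata, 30% smokers, baseline split at its median, 3,000 runs per cell (Monte Carlo SE about 0.8 points).
- Log-normal scores with mild skew (log SD 0.4), strong skew (0.8), or strong skew with about 15% zeros.
- Effect 0.564 residual SD, so the noncentrality is 0.564 x sqrt(50/2) = 2.82.

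Ranges are over the three shapes:

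| Baseline correlation | 0.3 | 0.5 | 0.7 |
|---|---|---|---|
| Wilcoxon power | 73-75% | 65-67% | 48-50% |
| Stratified Wilcoxon (van Elteren) power | 74-76% | 70-72% | 63-65% |
| Rank ANCOVA power | 77-78% | 75-77% | 75-76% |
| Log-ANCOVA power (constant 0.1) | 77-79% | 76-80% | 76-80% |
| Wilcoxon type I error | 4.3-4.7% | 3.0-3.6% | 1.7-1.9% |

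Rank ANCOVA's type I error was 4.4-5.4%. Wilcoxon falls below 5% because its variance ignores the balance that stratification has created.

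**Sensitivity to how the effect is scaled.** The first simulation fixes the effect in residual SD, so the total-scale effect shrinks as correlation rises. A second simulation fixed a log-scale effect of 0.5 SD and balanced smoking only. At R² = 0.10, 0.25 and 0.49:
- Wilcoxon power was 68%, 68% and 69%; rank ANCOVA 72%, 78% and 91%. The gaps are about 4, 10 and 22 points.
- Wilcoxon type I error was 4.6%, 4.6% and 3.3%.

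Across these and repeat runs, the gap was about 3-4, 9-12 and 21-28 points at correlations 0.3, 0.5 and 0.7.

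**Which result should govern.** In the first simulation, raw-scale and rank ANCOVA disagreed at the 5% level in 10-12% of runs with mild skew and 26-32% with strong skew. Under strong skew, with or without zeros, raw-scale ANCOVA power was 53-56%, 50-54% and 50-54% at the three correlations. At 0.3 and 0.5 that is below Wilcoxon itself: 0.750 - 0.562 = 0.19, 0.667 - 0.541 = 0.13, 0.729 - 0.534 = 0.20 and 0.648 - 0.495 = 0.15.

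**Constant before a log.** With zeros and correlation 0.5, log-ANCOVA power was 0.739, 0.758 and 0.688 for added constants 0.01, 0.1 and 1, a spread of 7 points.

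**The case against.** The strongest reply is that the plan already allows everything needed. Wilcoxon is introduced only as an example, a transformation is listed first and keeps the covariates, and an adjusted rank method is not excluded. That is right, so a reader who infers that the primary comparison will be unadjusted goes further than the text. What remains is that the only non-parametric method named is an unadjusted one, with nothing to steer the choice away from it.

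A reader might also infer that no adjusted means or intervals would be left. The documents do not say so. One of the two SAP statements of the fallback sits under supportive analyses, and nothing withdraws the ANCOVA table. Nor is it right that Wilcoxon can give no interval: Hodges-Lehmann supplies one, unadjusted. Rank ANCOVA itself gives no raw-scale means, so the raw-scale estimates must be kept in any case.

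The study is an exploratory proof of principle, not formally powered, with no multiplicity adjustment. No stated power target is therefore missed. It still reports p-values and intervals and sets a minimum requirement on stain, so precision matters.

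The stratifier is not the covariate: it is the facial total cut at 45, whereas the first simulation stratified on the covariate split at its median. The lowest type I error figures rest on that simplification. The 26-28 point gap in that simulation also depends on scaling the effect to residual SD; on a fixed effect the largest gap was 22.

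Finally, the general baseline definition in SAP 3.1 might be read as pointing to the post-prophylaxis zero check, which would make the covariate constant. SAP 4.4.1.2 and protocol 9.3.2 both specify pre-prophylaxis, so that reading is not supported and needs no action here.

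**Conclusion.** The point holds as a conditional loss of precision and a gap in pre-specification. If normality fails and the named non-parametric test is used, about 3-4, 9-12 or 21-28 points of power are given up against rank ANCOVA at assumed baseline correlations of 0.3, 0.5 or 0.7. The test also becomes conservative to a degree that depends on how well the strata track the outcome. It remains valid: a reader might infer bias, but randomisation protects against that and the documents give no ground for it.

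The direction was the same in every setting examined. The size rests on assumed correlation, skew, share of zeros, effect and smoking share, none of which the documents give. If baseline explains little of Week 4 stain, the loss is small; if a transformation is used, it need not arise at all. This is worth correcting before unblinding because it costs so little, but it is not a threat to the trial's validity.

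**What to change.** - In SAP 4.4.1.2, SAP 4.4.1.3 and protocol 9.3.2, replace the Wilcoxon example with a covariate-adjusted fallback: ANCOVA on the ranked Week 4 score with treatment, smoking status and ranked pre-prophylaxis baseline. The alternative is the same ANCOVA on a named transformation with any added constant fixed. A stratified Wilcoxon test would recover only part of the loss. If the protocol is not amended, record the change in SAP Section 5.
- Decide whether the fallback is needed, and which form, at the Blind Data Review Meeting that SAP Section 4 already schedules before database closure. Use pooled residuals from a model with baseline and smoking status and no treatment term, and record the decision.
- State that, once triggered, the fallback's p-value governs the comparison. Report the raw-scale ANCOVA adjusted means, differences and 95% CIs alongside as the descriptive effect, and state any disagreement. Letting the raw-scale p-value govern would defeat the purpose, since under strong assumed skew it had 13-20 points less power than Wilcoxon at correlations 0.3 and 0.5.

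The cost is three short text edits, possibly an entry in SAP Section 5, and a few lines of code. Data collection and sample size do not change. The drawback is that rank results are harder to read and may disagree with the raw-scale interval.
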